APPENDIX 9: Multicenter Institutional Studies

Data and Safety Monitoring Plan for Multicenter Study (Phase 2 or 3 Institutional Study)

The UCSF Helen Diller Family Comprehensive Cancer Center (HDFCCC) Data and Safety Monitoring Committee (DSMC) is responsible for monitoring data quality and subject safety for all HDFCCC institutional clinical studies. A summary of DSMC activities for this study include:

- Review of subject data
- Review of suspected adverse reactions considered “serious”
- Monitoring every six months (depending on study accrual)
- Minimum of a yearly regulatory audit

Monitoring and Reporting Guidelines

All institutional Phase 2 or 3 therapeutic studies are designated with a moderate risk assessment. The data is monitored every six months, with twenty percent of the subjects monitored (or at least three subjects if the calculated value is less than three).

The UCSF Coordinating Center provides administration, data management, and organizational support for the participating sites in the conduct of a multicenter clinical trial. The UCSF Coordinating Center will also coordinate quarterly conference calls with the participating sites to communicate the review of adverse events, safety data, and other study matters.

The Principal Investigator at the UCSF Coordinating Center will hold the role of Study Chair. The Study Chair is responsible for the overall conduct of the study and for monitoring its safety and progress at all participating sites. The Study Chair will conduct continuous review of data and subject safety and discuss each subject’s treatment at monthly UCSF Site Committee meetings. The discussions are documented in the UCSF Site Committee meeting minutes.

Multicenter communication

The UCSF Coordinating Center provides administration, data management, and organizational support for the participating sites in the conduct of a multicenter clinical trial. The UCSF Coordinating Center will also coordinate, at minimum, quarterly conference calls with the participating sites or more frequently as needed to discuss risk assessment. The following issues will be discussed as appropriate:

- Enrollment information
- Adverse Events (i.e. new adverse events and updates on unresolved adverse events and new safety information)
- Protocol Violations
- Other issues affecting the conduct of the study

Adverse events reporting to the DSMC will include reports from both the UCSF Coordinating Center, as well as the participating sites. The DSMC will be responsible for monitoring all data entered in OnCore® at the UCSF Coordinating Center and the participating sites. The data (i.e., copies of source documents) from the participating sites will be sent electronically to the UCSF Coordinating Center prior to the monitoring visits in order for the DSMC to remotely monitor the participating site’s compliance with the protocol, patient safety, and to verify data entry.

Adverse Event Review and Monitoring

All grade(s) 3-5 adverse events, whether or not unexpected, and whether or not considered to be associated with the use of the study drug, will be entered into OnCore®, UCSF's Clinical Trial Management System.

All Grade 3-5 adverse events entered into OnCore® will be reviewed on a monthly basis at the UCSF Site Committee meetings. All clinically significant adverse events must be reported to the UCSF Coordinating Center by the participating sites within 10 business days of becoming aware of the event or during the next scheduled quarterly conference call, whichever is sooner. The UCSF Site Committee will review and discuss the selected toxicity, the toxicity grade, and the attribution of relationship of the adverse event to the administration of the study drug(s) from the UCSF Coordinating Center and the participating sites.

In addition, all suspected adverse reactions considered “serious” must be entered in OnCore® and reported to the UCSF Coordinating Center within 1 business day. The suspected adverse reactions considered “serious” will be reviewed and monitored by the Data and Safety Monitoring Committee on an ongoing basis and discussed at the DSMC meeting, which take place every six (6) weeks.

If a death occurs during the treatment phase of the study or within 30 days after the last administration of the study drug(s) and is determined to be related either to the investigational drug or any research related procedure, the Study Chair at the UCSF Coordinating Center or the assigned designee must be notified within 1 business day from the participating site(s) and the Study Chair must then notify the DSMC Chair or qualified alternate within 1 business day of this notification. The contact may be by phone or e-mail.

Increase in Adverse Event Rates

If an increase in the frequency of Grade 3 or 4 adverse events (above the rate reported in the Investigator Brochure or package insert) is noted in the study, the Study Chair at the UCSF Coordinating Center is responsible for notifying the DSMC at the time the increased rate is identified. The report will indicate if the incidence of adverse events observed in the study is above the range stated in the Investigator Brochure or package insert.

If at any time the Study Chair stops enrollment or stops the study due to safety issues, the DSMC Chair and DSMC Manager must be notified within 1 business day via e-mail. The DSMC must receive a formal letter within 10 business days and the IRB must be notified.

Data and Safety Monitoring Committee Contacts

DSMC

Chair:

Phone:

Email:

Address:

[REDACTED]
[REDACTED]
[REDACTED]
[REDACTED]
UCSF
San Francisco, CA 94115

DSMC Monitors

[REDACTED]
UCSF Helen Diller Family
Comprehensive Cancer Center
San Francisco, CA 94115

* DSMP approved by NCI 09/February2012

APPENDIX 10: UCSF Policy/Procedure for Required Regulatory Documents for UCSF Investigator-Initiated Oncology Clinical Trials with an Investigator held Investigational New Drug (IND)

Purpose

This policy defines the required Regulatory Documents for Single Site and Multicenter Investigator Initiated Oncology Clinical Trials at the Helen Diller Family Comprehensive Cancer Center (HDFCCC) where the Principal Investigator (PI) holds the IND.

Background

The International Conference on Harmonization (ICH) Good Clinical Practices (GCP) Guidelines define Essential Regulatory Documents as those documents which individually and collectively permit evaluation of the conduct of a trial and the quality of data produced. These documents serve to demonstrate compliance with standards of GCP and with all applicable regulatory requirements. Filing essential documents in a timely manner can greatly assist in the successful management of a clinical trial.

The Regulatory Documents will consist of electronic files in both iMedRIS and OnCore[®], as well as paper files in the Regulatory Binders for both the Coordinating Site and the Participating Site(s) in the HDFCCC Investigator Initiated Oncology Clinical Trials.

Procedures

1. HDFCCC Essential Regulatory Documents

Documents Filed in iMedRIS:

- IRB approvals for initial submission of application, all modifications, and continuing annual renewals
- Current and prior approved protocol versions with signed protocol signature page(s)
- Institutional Review Board (IRB) approval letters and Informed Consent Form(s) (ICF)
- Current and prior versions of the Investigator Brochure (IB).
- Serious Adverse Event Reporting
- Protocol Violations and Single Patient Exception (SPE) Reports to IRB with supporting fax documentation

Documents Filed in OnCore[®]:

- Package Insert (if the study drug is commercial) or Investigator Brochure
- Protocol Review Committee (PRC) approved protocols, protocol amendments and Summary of Changes (SOC)
- Patient handouts
- Screening/enrollment log
- Data and Safety Monitoring Committee (DSMC) monitoring reports
- OnCore[®] Case Report Form (CRF) completion manual

Documents Filed in Regulatory Binder:

- Completed Food and Drug Administration (FDA) 1572 document with Study Chair's signature
- For all Study Chair and Sub-Investigators listed on the FDA 1572, will need Financial Disclosure Forms, CVs, MD Licenses, Drug Enforcement Agency (DEA) Licenses, and Staff Training Documents (i.e. Collaborative Institute Training Initiative (CITI), etc.)
- Site Initiation Visit (SIV) minutes and correspondence with participating site(s).
- As applicable, approvals for Biosafety Committee, Radiation Committee, and Infusion Center
- Serious Adverse Event (SAE) reports to IRB and sponsor.
- MedWatch reporting to sponsor
- Delegation of Authority Form
- Drug Destruction Standard Operating Procedure (SOP)
- For all laboratories listed on the FDA 1572, will need CLIA certifications, CAP certifications, lab licenses, CVs of Lab Directors, and laboratory reference ranges

2. *Additional Essential Documents for Multicenter Trials for the Coordinating Center (filed in Regulatory Binder or OnCore)*

- Institutional Review Board (IRB) approval letters, IRB roster, Informed Consent Form (ICF), and Health Insurance Portability and Accountability Act (HIPAA) Consent Form for the Participating Site(s)
- For all Principal Investigators and Sub-Investigators listed on the 1572 at the Participating Site(s) – Financial Disclosure Forms, CVs, MD Licenses, and Staff Training documents (i.e. Collaborative Institute Training Initiative (CITI), etc.) for Investigational New Drug Application
- Site Initiation Visit (SIV) minutes and correspondence with Participating Site(s).
- As applicable, approvals for Biosafety Committee, Radiation Committee, and Infusion Center for the Participating Site(s)
- Protocol Violations and Single Patient Exception (SPE) reports to IRB with supporting fax documentation for Participating Site(s)
- Drug Destruction Standard Operating Procedure (SOP) for the Participating Site(s)
- Data and Safety Monitoring Committee (DSMC) monitoring reports for the Participating Site(s)
- For all laboratories listed on FDA 1572, will need CLIA certifications, CAP certifications, lab licenses, CVs of Lab Directors, and laboratory reference ranges for the Participating Site(s)
- Copy of the Data and Safety Monitoring Plan (DSMP) Monitoring Plan for all participating site(s) in Multicenter studies or Contract Research Organization (CRO) Monitoring Plan (if an outside CRO is used for the study)
- Serious Adverse Event (SAE) forms submitted to both the IRB and the sponsor for the Participating Site(s)

Required Regulatory Documents for Sub-sites Participating in a UCSF Investigator Initiated Multicenter Trial (Checklist)

Directions:

- 1) Fax the documents listed below to the UCSF Coordinating center [REDACTED] *or*
- 2) Scan the documents and upload to OnCore® and create a Note to File for the on-site Regulatory binder to indicate where these documents may be found

1572

PI and Sub investigators:
CV and Medical license
Financial disclosure form
NIH or CITI human subject protection training certification

Laboratories
CLIA and CAP
CV of Lab Director and Lab Licenses
Laboratory reference ranges

Local Institutional Review Board

IRB Approval letter
 Reviewed/Approved documents

- Protocol version date: _____
- Informed consent version date: _____
- Investigator Brochure version date: _____
- HIPAA

Current IRB Roster

Other

Delegation of Authority Log

- Include NIH or CITI human subject protection training certificates or GCP training certification

Pharmacy

- Drug destruction SOP and Policy

Protocol signature page

Executed sub contract

APPENDIX 11: DENDREON SAE FORM

SERIOUS ADVERSE EVENT FORM

**FAX TO DENDREON DRUG SAFETY WITHIN 24 HOURS
OF BECOMING AWARE OF EVENT: [contact]**

SERIOUS ADVERSE EVENT FORM

FAX TO DENDREON DRUG SAFETY WITHIN 24 HOURS
OF BECOMING AWARE OF EVENT: [contact]

Section 1b

SUBJECT #: _____

SUBJECT INITIALS:

Section 7

CASE NARRATIVE:

Describe the SAE. Include presenting signs and symptoms, clinical cause of the event, treatment of the event, and any other assessments which help explain the event. Give duration of the event if it persisted for less than 24 hours. State whether the event is or is not related to the apheresis procedure or investigational product infusion.

Section 8

OTHER RELEVANT HISTORY, TESTS OR LABORATORY DATA, CONCOMITANT MEDICATIONS OR THERAPY:

For example: cancer, allergies or concurrent illnesses. Attach relevant laboratory and imaging results. Attach updated Concomitant Medications CRF.

Section 9 INITIAL REPORT

INVESTIGATOR SIGNATURE: _____

DATE: / /
MM DD YY

FOLLOW-UP REPORTS

INVESTIGATOR INITIALS: _____ DATE: / / INVESTIGATOR INITIALS: _____ DATE: / / INVESTIGATOR INITIALS: _____ DATE: / /
MM DD YY

APPENDIX 12: IRRC TUMOR MEASUREMENT FORM

CC#12257 Ipi- Provence (Phase 2) - Tumor Assessment Form

Protocol version date: March 26, 2014

Name:	Subject ID:	MRN:	DOB:
-------	-------------	------	------

Immune- related Response Criteria Instructions

- Measurable Disease/Target Lesions: longest diameter (LD) and longest perpendicular (LP), must be ≥ 20 mm with conventional techniques or ≥ 10 mm with spiral CT scan.
- Non-measurable disease/Non-Target Lesions: all other lesions that do not qualify as target lesions, including small lesions, longest diameter < 20 mm with conventional techniques or < 10 mm with spiral CT scan and truly non-measurable lesions such as bone lesions)
- Add up to a maximum of 5 lesions per organ and 10 lesions total, representative of all involved organs
- $LD(cm) \times LP(cm) = PD(cm^2)$: Longest diameter x longest perpendicular = product of perpendicular diameters (PPD).
- SPD: Sum of products of the two largest perpendicular diameters.
- At each subsequent tumor assessment, the SPD of the index lesions and of new measurable lesions ($\geq 5 \times 5$ mm; up to 5 new lesions per organ, 10 visceral lesions) are added together to provide the total tumor burden.

Tumor Burden = $SPD_{\text{index lesions}} + SPD_{\text{new measurable lesions}}$

- New non- measurable lesions should be added to non-measurable index lesions.
- Target lesions overall response (CR, PR, and PD must be confirmed by a repeat, consecutive assessment no less than 4 wks from the date first documented):
 - Complete Response (CR): disappearance of all lesions (whether measurable or not, and no new lesions)
 - Partial response (PR): decrease in tumor burden $\geq 50\%$ relative to baseline
 - Stable Disease (SD): not meeting criteria for CR or PR, in absence of PD
 - Progressive Disease (PD): increase in tumor burden $\geq 25\%$ relative to nadir
- Non-target lesions overall response
 - CR: The disappearance of all non-target lesions
 - IR/SD: the persistence of one or more non-target lesion(s) without unequivocal progression of existing non-target lesions
 - PD: the appearance of one more or more new lesions and/or unequivocal progression of existing non-target lesions. For bone scans, the appearance of 2 or more new lesions is required. These lesions should be re-evaluated 6 or more weeks later to confirm PD

Date:	BASELINE	DAY 64	DAY 148	DAY 232

TARGET LESIONS

#	Location	Method of Measurement	LD x LP = PPD			
1						
2						
3						
4						
5						
6						
7						
8						
9						
10						

*Tumor Burden =
 $SPD_{\text{index lesions}} + SPD_{\text{new measurable lesions}}$

Sum of PPD (SPD)/
Tumor Burden*

% change: N/A

NON-TARGET LESIONS

#	Location	Method of Measurement	BASELINE	DAY 64	DAY 148	DAY 232
1						
2						
3						
4						
5						
6						
7						
8						
9						
10						

OVERALL RESPONSE ASSESSMENT (circle one)

N/A CR IR/SD PD CR IR/SD PD CR IR/SD PD

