Our trial design of studying sequential treatment with ipilimumab following SipT represents the schedule that is currently clinically feasible. No data are available as to whether the presence of ipilimumab within a patient may alter the SipT product. Because the SipT product has specific release criteria, SipT treatment will be completed prior to treatment with ipilimumab in order to not jeopardize the production of the SipT.

PSA decline of > 50% was chosen as a secondary endpoint of this study given the difficulty of evaluating prostate cancer patients radiographically. Metastatic disease is primarily unmeasurable and bone scans rarely show the improvement that would reflect response and clinical benefit. To include only patients with measurable disease would limit the applicability of this therapy to a very limited subset of patients. Although PSA decline is not a widely accepted surrogate endpoint, it is often used as the primary endpoint in clinical studies.

Results from efficacy studies of ipilimumab in advanced melanoma have shown both the 3 and 10 mg/kg ipilimumab doses are safe and effective. Ipilimumab was approved in US and Europe at a dose of 3 mg/kg in adults patients with advanced melanoma based on a phase 3 study in patients with previously treated melanoma (MDX010-20). Ipilimumab 10 mg/kg was used in a second registrational study in adult patients with previously untreated advanced melanoma and prolonged overall survival when combined with DTIC, versus DTIC alone (CA184-024). A randomized phase 2 study in advanced melanoma (CA184-022) suggested that 10 mg/kg ipilimumab was potentially more active and was associated with increased toxicities relative to 3 mg/kg dose. An ongoing phase 3 trial (CA184169) of 3 vs. 10 mg/kg ipilimumab will provide definitive answer regarding whether there is an optimal monotherapy dose in advanced melanoma.

The dosing interval for ipilimumab is based on the prior study which demonstrated drug levels \geq 10 mg/mL (a minimum level required for CTLA-4 blockade in pre-clinical models) for greater than 28 days. Four doses of ipilimumab given every 3 weeks were chosen because four doses have been given safely in other trials.

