7.1.3 Clinical Efficacy Evaluation

Patients will have PSA measurements on day 1 of every cycle prior to treatment. PSA decline will be evaluated according to the recommendations from PSA Working Group (PSAWG)³⁹. Although response in this study is defined as a PSA decline, progressive disease is defined as progression by either PSA or objective progression. Bone scans and CT scans will be repeated every 12 weeks and at the time of PSA progression. Each category (measurable, non-measurable, and PSA) will be assessed and reported independently. Measurable disease/target lesions and non-measurable disease/non-target lesions will be evaluated according to the irRC.⁹

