9.3.2.2 Radiographic Clinical Responses

For each treatment arm, for patients with objective disease, using immune-related response criteria (irRC) criteria, the proportion of patients achieving a complete or partial response will be determined and reported with 95% confidence intervals.

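### The overall response row on the Appendix 12 tumor form has no PR option, although the radiographic endpoint counts CR plus PR

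*Combined protocol and SAP*

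**What the plan says.** Section 9.3.2.2 sets the radiographic endpoint: for patients with objective disease in each arm, using irRC, "the proportion of patients achieving a complete or partial response will be determined and reported with 95% confidence intervals".

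Section 7.1.3.2 bases overall irRC response on tumor burden, meaning the SPD of the index lesions plus that of new measurable lesions, with four outcomes: CR, PR, SD and PD. PR is a decrease of at least 50% from baseline, confirmed at least 4 weeks later. CR requires every lesion to disappear, measurable or not.

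The instructions in Appendix 12 carry two scales. The first begins "Target lesions overall response (CR, PR, and PD must be confirmed by a repeat, consecutive assessment" and includes "Partial response (PR): decrease in tumor burden" of at least 50% from baseline. The second is for non-target lesions. It begins "CR: The disappearance of all non-target lesions" and continues with IR/SD and PD only.

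Below the non-target table the form prints one field, "OVERALL RESPONSE ASSESSMENT (circle one"), with the options "N/A CR IR/SD PD CR IR/SD PD CR IR/SD PD".

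Section 7.1.3 adds: "Each category (measurable, non-measurable, and PSA) will be assessed and reported independently".

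**The concern.** The field is labelled as the overall response but carries the non-target categories. A patient whose tumor burden has halved is a PR by section 7.1.3.2 and by the form's own instructions, yet must be circled CR, IR/SD or PD, none of which is right.

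PR matters in this population. CR needs all lesions to clear, bone lesions included, and section 1.3 says that "bone scans rarely show the improvement that would reflect response and clinical benefit". For men with bone disease, PR is the more reachable of the two responses that the endpoint counts.

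The row can also mislead in the other direction. If non-target lesions clear while target lesions are only stable, a reader who takes the label at its word could record an overall CR.

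Radiographic response per arm is a named secondary measure of clinical activity. Section 10.4 requires case report form entries to match the source documents. If this form serves as source, a PR in the database would sit beside a circled IR/SD labelled as the overall response.

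**Working it through.** The plan states no figure for this endpoint: no null rate, target rate or power. The check is therefore a comparison of text, followed by an illustration.

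**Step 1. Categories required and categories offered.**

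| Place | Categories |
|---|---|
| 9.3.2.2, endpoint | counts CR and PR |
| 7.1.3.2, irRC on tumor burden | CR, PR, SD, PD |
| Appendix 12 instructions, target lesions | CR, PR, SD, PD |
| Appendix 12 instructions, non-target lesions | CR, IR/SD, PD |
| Appendix 12, overall response row | CR, IR/SD, PD |

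The row reads N/A under baseline, then the same three options under each of Day 64, Day 148 and Day 232. PR appears 0 times. The row matches the non-target scale exactly.

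**Step 2. An example.** Take two nodes, 20 x 20 mm and 15 x 15 mm, shrinking to 10 x 10 mm and 8 x 8 mm.

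- Baseline SPD = 2.0 x 2.0 + 1.5 x 1.5 = 6.25 cm²
- Follow-up SPD = 1.0 x 1.0 + 0.8 x 0.8 = 1.64 cm²
- Change = (1.64 − 6.25) / 6.25 = −73.8%

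With confirmation this is a PR. If bone lesions persist without progression, the option that fits on the form is IR/SD.

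**Step 3. Is PR recoverable?** The form has fields for the product of diameters of each lesion, the SPD or tumor burden, and the percent change at each visit. Section 7.1.3.2 needs tumor burden and visit dates, so the PR in step 2 can be derived from recorded data whatever was circled.

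**Step 4. Size if the circled row alone were analysed.** The number of patients with measurable disease and the number of PRs are not stated. Assume 0 CR and 2 PR per arm and vary the denominator n up to the 27 evaluable patients planned. Exact Clopper-Pearson limits for x responders are Beta(0.025; x, n − x + 1) and Beta(0.975; x + 1, n − x); for x = 0 the lower limit is 0.

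| n (assumed) | CR + PR from tumor burden | From the circled row |
|---|---|---|
| 10 | 2/10 = 20.0% (2.5 to 55.6) | 0% (0 to 30.8) |
| 15 | 2/15 = 13.3% (1.7 to 40.5) | 0% (0 to 21.8) |
| 20 | 2/20 = 10.0% (1.2 to 31.7) | 0% (0 to 16.8) |
| 27 | 2/27 = 7.4% (0.9 to 24.3) | 0% (0 to 12.8) |

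In general, the rate falls from (CR + PR)/n to CR/n. The table shows what that fall would look like; it does not predict it.

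**The case against.** A reader might infer that partial responders will drop out of the endpoint. The documents do not support that. Section 7.1.3.2 derives irRC response from tumor burden, 9.3.2.2 uses irRC, and the form collects the measurements needed. No section makes the circled category the analysis value, and the case report forms named in section 10.4 are not reproduced in the documents. This part of the objection stands in full.

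The row may also simply be a mislabelled non-target row. It sits under the non-target table, uses that scale, and the instructions head that scale as an overall response for non-target lesions. On this reading IR/SD for non-target lesions is compatible with PR on target lesions, and the form is closer to the separate reporting required by 7.1.3. This is plausible. But the label is then wrong, and no visible field records target-lesion response, which is the category the endpoint uses. The same repair is needed.

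A target-response row may have been lost when the form was converted from PDF. That cannot be excluded, because the layout is visibly flattened. The surviving row is complete in itself, so its label and its missing PR would still need correcting.

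The practical effect may be small. Section 1.2.4 describes tumor shrinkage as infrequent in an earlier vaccine combination with ipilimumab, and section 4.2 excludes known visceral metastases. That stands, and it is a reason not to put a size on the loss.

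Finally, the single percent-change line does not say whether it refers to baseline or nadir. The form's instructions already give baseline for PR and nadir for PD, so splitting that line is a matter of preference and is not part of this point.

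**Conclusion.** As printed, the overall response field cannot record a partial response, while the form's target-lesion instructions, section 7.1.3.2 and the endpoint in 9.3.2.2 all require one. That much is certain from the visible text, subject to checking the original page for a target-response row.

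The harm is conditional. If the circled category were analysed, the reported rate would reduce to CR alone, and a non-target clearance could be miscounted as an overall CR. If response is derived from recorded tumor burden, PR is kept. The documents do not say which field feeds the endpoint, and they give neither the number of patients with measurable disease nor an expected PR rate, so the size of any bias is unknown. It would be wrong to conclude that PR information is lost or that the response rate is necessarily biased toward zero.

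The point concerns a descriptive secondary endpoint. The primary IgG endpoint and its sample size are unaffected. The correction should be made before the radiographic analysis because it is cheap and closes a route to misclassification.

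**What to change.** First check the original Appendix 12 page for a target-lesion response row. Then:

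1. Relabel the existing row *Non-target lesion response*, keeping CR, IR/SD and PD.
2. Add, if it is absent, a row *Target-lesion irRC response* for each post-baseline visit, with CR, PR, SD, PD and not evaluable.
3. Add to 9.3.2.2: *The CR plus PR endpoint is derived from the recorded tumor burden (SPD), with confirmation as defined in 7.1.3.2. This applies also to forms already completed, whatever category was circled.*

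The cost is one revised form page, one short addition to the analysis section, and a programmed derivation from measurements the form already collects. No new scans, patients or readers are needed.
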